5.2.2 Timing of Dose Administration

All trial treatments will be administered on an outpatient basis.

ADV/HSV-tk (5×10^{11} vp) in a 2-mL total volume will be injected intratumorally on Day 0 of the study. For nodal, lung, and liver lesions, ADV/HSV-tk will be administered after fiducial placement for SBRT.

Valacyclovir will be orally administered at a dose of 2 g t.i.d. for 14 days from Day 1 to Day 15 of the study.

Primary lung tumors and metastatic lesions (breast and lung) will be treated with SBRT (30 Gy; 6 Gy X 5 fractions). Primary breast tumors will be treated with a short course (5–8 fractions) of 3D RT. SBRT and 3D RT will be administered over 2 weeks from Day 2 to Day 16 of the study.

Pembrolizumab 200 mg will be administered as a 30 minute IV infusion Q3W (\pm 1 day). Sites should make every effort to target infusion timing to be as close to 30 minutes as possible. However, given the variability of infusion pumps from site to site, a window of -5 minutes and +10 minutes is permitted (i.e., infusion time is 30 minutes: -5 min/+10 min).

The Pharmacy Manual contains specific instructions for the preparation of the pembrolizumab infusion fluid and administration of infusion solution.

5.2.3 Second Course

All subjects who stop pembrolizumab treatment with CR may be eligible for up to an additional 12 months (17 cycles) of pembrolizumab treatment if they progress after stopping pembrolizumab from the initial treatment phase. This retreatment is termed the Second Course Phase of this trial and is only available if the trial remains open and the subject meets the following conditions:

Either

- Stopped initial treatment with pembrolizumab after attaining an investigator-determined confirmed CR based on the RECIST 1.1, and
 - Was treated with at least 8 cycles of pembrolizumab before discontinuing treatment, and
 - Received at least 2 cycles of pembrolizumab beyond the date when the initial CR was declared

OR

- Had CR and stopped pembrolizumab treatment after completion of 24 months (35 cycles) of pembrolizumab for reasons other than disease progression or intolerability

AND

- Experienced an investigator-determined radiographic disease progression by the RECIST 1.1 after stopping initial pembrolizumab treatment, and
 - No new anticancer treatment was administered after the last dose of pembrolizumab, and

- The subject meets all of the safety parameters listed in the inclusion criteria and none of the safety parameters listed in the exclusion criteria, and
- The study is ongoing

An objective response or disease progression that occurs during the Second Course Phase for a subject will not be counted as an event for the primary analysis of either endpoint in this trial.

5.2.4 Trial Blinding/Masking

This is an open label trial; therefore, the Sponsor, investigator, and subject will know the treatment administered.

5.3 Concomitant Medications/Vaccinations (allowed & prohibited)

Medications or vaccinations specifically prohibited in the exclusion criteria are not allowed during the ongoing trial. If there is a clinical indication for one of these or other medications or vaccinations specifically prohibited during the trial, discontinuation from trial therapy or vaccination may be required. The investigator should discuss any questions regarding this with the Merck Clinical team. The final decision on any supportive therapy or vaccination rests with the investigator and/or the subject's primary physician.

5.3.1 Acceptable Concomitant Medications

All treatments that the investigator considers necessary for a subject's welfare may be administered at the discretion of the investigator in keeping with the community standards of medical care. All concomitant medication will be recorded on the CRF including all prescription, over-the-counter, herbal supplements, and IV medications and fluids. If changes occur during the trial period, documentation of drug dosage, frequency, route, and date may also be included on the CRF.

All concomitant medications received within 28 days before the first dose of trial treatment and 30 days after the last dose of trial treatment should be recorded. Concomitant medications administered 30 days after the last dose of trial treatment should be recorded for SAEs and events of clinical interest (ECIs) as defined in Section 7.2.

5.3.2 Prohibited Concomitant Medications/Therapies

Subjects are prohibited from receiving the following until disease progression is documented per modified irRC and RECIST 1.1:

- Antineoplastic systemic chemotherapy, hormone therapy, or targeted/biological therapy.
- Immunotherapy not specified in this protocol.
- RT not specified in this protocol.

NOTE: Patients are allowed to have palliative radiotherapy to a painful site if they are otherwise benefitting from the trial treatment per the treating physician's judgment and and it is not the target index lesion for tumor response assessment.

- Investigational agents other than pembrolizumab and ADV/HSV-tk.

Live vaccines within 30 days prior to the first dose of trial treatment and while participating in the trial. Examples of live vaccines include, but are not limited to, the following: measles, mumps, rubella, varicella/zoster, yellow fever, rabies, bacillus Calmette-Guérin, and typhoid vaccine.

- Systemic glucocorticoids for any purpose other than to modulate symptoms from an ECI of suspected immunologic etiology. The use of physiologic doses of corticosteroids may be approved after consultation with the Sponsor.

Subjects who, in the assessment by the investigator, require the use of any of the aforementioned treatments for clinical management should be removed from the trial. Subjects may receive other medications that the investigator deems to be medically necessary.

The Exclusion Criteria describes other medications that are prohibited in this trial.

There are no prohibited therapies during the Post-Treatment Follow-up Phase.

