5.2.1.2 Dose Modification

Pembrolizumab: AEs (both non-serious and serious) associated with pembrolizumab exposure may represent an immunologic etiology. These AEs may occur shortly after the first dose or several months after the last treatment dose. Pembrolizumab must be withheld for drug-related toxicities and severe or life-threatening AEs as per Table 3 below. See Section 5.4 for supportive care guidelines, including use of corticosteroids.

Table 3 Dose Modification Guidelines for Pembrolizumab-Related AEs

Toxicity	Hold Treatment For Grade	Timing for Restarting Treatment	Treatment Discontinuation
Diarrhea/Colitis	2-3	Toxicity resolves to Grade 0-1	Toxicity does not resolve within 12 weeks of last dose or inability to reduce corticosteroid to 10 mg or less of prednisone or equivalent per day within 12 weeks
	4	Permanently discontinue	Permanently discontinue
Increased AST, ALT, or Bilirubin	2	Toxicity resolves to Grade 0-1	Toxicity does not resolve within 12 weeks of last dose
	3-4	Permanently discontinue (see exception below) ^a	Permanently discontinue
Type 1 Diabetes Mellitus (T1DM; if new onset) or Hyperglycemia	T1DM or 3-4	Hold pembrolizumab for new onset T1DM or Grade 3-4 hyperglycemia associated with evidence of beta cell failure	Resume pembrolizumab when patients are clinically and metabolically stable
Hypophysitis	2-4	Toxicity resolves to Grade 0-1. Therapy with pembrolizumab can be continued while endocrine replacement therapy is instituted	Toxicity does not resolve within 12 weeks of last dose or inability to reduce corticosteroid to 10 mg or less of prednisone or equivalent per day within 12 weeks
Hyperthyroidism	3	Toxicity resolves to Grade 0-1	Toxicity does not resolve within 12 weeks of last dose or inability to reduce corticosteroid to 10 mg or less of prednisone or equivalent per day within 12 weeks
	4	Permanently discontinue	Permanently discontinue
Hypothyroidism		Therapy with pembrolizumab can be continued while thyroid replacement therapy is instituted	Therapy with pembrolizumab can be continued while thyroid replacement therapy is instituted
Infusion Reaction	2 ^b	Toxicity resolves to Grade 0-1	Permanently discontinue if toxicity develops despite adequate premedication
	3-4	Permanently discontinue	Permanently discontinue
Pneumonitis	2	Toxicity resolves to Grade 0-1	Toxicity does not resolve within 12 weeks of last dose or inability to reduce corticosteroid to 10 mg or less of prednisone or equivalent per day within 12 weeks

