5.4 Rescue Medications & Supportive Care

5.4.1 Supportive Care Guidelines

Subjects should receive appropriate supportive care measures as deemed necessary by the treating investigator. Suggested supportive care measures for the management of AEs with potential immunologic etiology are outlined below. Where appropriate, these guidelines include the use of oral or IV treatment with corticosteroids as well as additional anti-inflammatory agents if symptoms do not improve with administration of corticosteroids. Note that several courses of steroid tapering may be necessary as symptoms may worsen when the steroid dose is decreased. For each disorder, attempts should be made to rule out other causes such as metastatic disease or bacterial or viral infection, which might require additional supportive care. The treatment guidelines are intended to be applied when the investigator determines the events to be related to pembrolizumab.

Note: if after the evaluation the event is determined not to be related, the investigator does not need to follow the treatment guidance (as outlined below). Refer to Section 5.2.1.2 for dose modification.

It may be necessary to perform conditional procedures such as bronchoscopy, endoscopy, or skin photography as part of evaluation of the event.

- **Pneumonitis:**

- For **Grade 2 events**, treat with systemic corticosteroids. When symptoms improve to Grade 1 or less, steroid taper should be started and continued over no less than 4 weeks.
- For **Grade 3–4 events**, immediately treat with IV steroids. Administer additional anti-inflammatory measures as needed.
- Add prophylactic antibiotics for opportunistic infections in the case of prolonged steroid administration.

- **Diarrhea/Colitis:**

Subjects should be carefully monitored for signs and symptoms of enterocolitis (such as diarrhea, abdominal pain, blood or mucus in stool, with or without fever) and of bowel perforation (such as peritoneal signs and ileus).

- All subjects who experience diarrhea/colitis should be advised to drink liberal quantities of clear fluids. If sufficient oral fluid intake is not feasible, fluid and electrolytes should be substituted via IV infusion. For Grade 2 or higher diarrhea, consider gastrointestinal consultation and endoscopy to confirm or rule out colitis.
- For **Grade 2 diarrhea/colitis**, administer oral corticosteroids.
- For **Grade 3 or 4 diarrhea/colitis**, treat with IV steroids followed by HD oral steroids.

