7.2.3.2 Events of Clinical Interest

Selected non-serious and serious AEs are also known as ECI and must be reported within 24 hours to the Sponsor ([contact]; [contact]) and within 2 working days to Merck Global Safety (Attn: Worldwide Product Safety; [contact]).

From the time of informed consent form signing, any ECI or follow up to an ECI that occurs to any subject must be reported within 24 hours to the Sponsor and within 2 working days to Merck Global Safety if it causes the subject to be excluded from the trial or is the result of a protocol-specified intervention, including but not limited to washout or discontinuation of usual therapy, diet, placebo treatment, or a procedure.

From the time of informed consent form signing through 90 days following cessation of treatment or 30 days following cessation of treatment if the subject initiates new anticancer therapy, whichever is earlier, any ECI or follow up to an ECI, whether or not related to the study treatment, must be reported within 24 hours to the Sponsor and within 24 hours to Merck Global Safety.

ECIs for this trial include:

1. an overdose of pembrolizumab, as defined in Section 7.2.1 - Definition of an Overdose for This Protocol and Reporting of Overdose to the Sponsor, that is not associated with clinical symptoms or abnormal laboratory results.
2. an elevated AST or ALT lab value that is greater than or equal to 3 X ULN and an elevated total bilirubin lab value that is greater than or equal to 2 X ULN and, at the same time, an alkaline phosphatase lab value that is less than 2 X ULN, as determined by way of protocol-specified laboratory testing or unscheduled laboratory testing.*

*Note: These criteria are based upon available regulatory guidance documents. The purpose of the criteria is to specify a threshold of abnormal hepatic tests that may require an additional evaluation for an underlying etiology.

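### Section 5.3.2 ties permitted steroid use to an ECI list that omits nearly all the immune events for which Section 5.4.1 directs steroids, so the rules for Grade 2 events conflict

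*Combined protocol and SAP*

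**What the plan says.** Section 5.3.2 lists treatments prohibited until progression is documented. One entry is "Systemic glucocorticoids for any purpose other than to modulate symptoms from an ECI of suspected immunologic etiology". A second exception follows: "The use of physiologic doses of corticosteroids may be approved after consultation with the Sponsor". Subjects who, in the investigator's assessment, "require the use of any of the aforementioned treatments for clinical management should be removed from the trial". The parent Section 5.3 is softer: where a prohibited medication is indicated, "discontinuation from trial therapy or vaccination may be required".

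Section 5.3.1 points to Section 7.2 for the definition of an ECI. Section 7.2.3.2 introduces its list with "ECIs for this trial include" and gives two items: a pembrolizumab overdose without symptoms or abnormal laboratory results, and AST or ALT at least 3 x ULN with total bilirubin at least 2 x ULN and, at the same time, alkaline phosphatase below 2 x ULN.

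Section 5.4.1 gives steroid guidance for adverse events of potential immunologic origin. For Grade 2 pneumonitis the instruction is to "treat with systemic corticosteroids. When symptoms improve to Grade 1 or less, steroid taper should be started". Section 5.2.1.2 refers to Section 5.4 for steroid use. Table 3 there holds pembrolizumab and allows restart on resolution to Grade 0-1; for several events one ground for stopping is "inability to reduce corticosteroid to 10 mg or less of prednisone or equivalent per day within 12 weeks".

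**The concern.** Read with the trial's own ECI definition, Section 5.3.2 does not permit most of the steroid treatment that Section 5.4.1 directs and Table 3 takes for granted. A patient with Grade 2 pneumonitis is given systemic steroids under 5.4.1, may restart pembrolizumab under Table 3, and should be removed from the trial under 5.3.2. Two investigators who each follow the document could handle the same event differently.

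For the analysis, whether treatment continues after an immune event would depend on which section was applied. Section 8.1 commits to reporting the frequency of dose interruptions and of toxicity-related treatment discontinuation; the second of these would partly reflect how 5.3.2 was read. Section 8 does not say how patients removed from the trial are counted.

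**Working it through.** The plan has no figure to reproduce. The check sets the provisions side by side.

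**Step 1. Does any ECI cover the steroid-treated events?** Section 5.4.1 directs steroids for six event groups: pneumonitis, diarrhea/colitis, hypophysitis, Grade 3-4 hyperthyroidism, hepatic events, and renal failure or nephritis. Of the two ECIs, only the liver-test pattern could be immune-mediated. Five of the six groups therefore have no matching ECI. The hepatic group matches only when all three laboratory conditions hold together, whereas 5.4.1 directs steroids for any Grade 2 hepatic event considered related to pembrolizumab. No other use of the term ECI in the document adds an immune event.

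**Step 2. Grade 2 events.**

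| Grade 2 event | Section 5.4.1 | Table 3 | On ECI list? | Section 5.3.2 read literally |
|---|---|---|---|---|
| Pneumonitis | steroids | hold, may restart | no | should be removed |
| Diarrhea/colitis | steroids | hold, may restart | no | should be removed |
| Hypophysitis | steroids | hold, may restart | no | should be removed |
| Renal failure/nephritis | steroids | hold, may restart | no | should be removed |
| Hepatic | steroids | hold, may restart | only if the combined pattern is met | should be removed unless the pattern is met |

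**Step 3. Where does 5.3.2 change nothing?**
- Section 5.6 already discontinues Grade 3 or 4 immune-mediated complications. Hyperthyroidism drops out, because 5.4.1 directs steroids for it only at Grade 3-4.
- Sections 5.2.1.2 and 5.6 discontinue patients whose interruption exceeds 21 days.
- Type 1 diabetes/hyperglycemia, hypothyroidism and Grade 2 hyperthyroidism carry no steroid instruction.

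What remains is the five rows above, with interruptions of 21 days or less.

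**Step 4. Related conflicts with Table 3.** Table 3 allows restart after Grade 3 diarrhea/colitis, Grade 3-4 hypophysitis, Grade 3 hyperthyroidism and other Grade 3 drug-related toxicity, while 5.6 discontinues Grade 3-4 immune-mediated complications. Table 3 also works with 12 weeks from the last dose. The 21-day limit runs from the intended dosing day, which on a 3-week schedule is 21 + 21 = 42 days, or 6 weeks, from the last dose. Amending 5.3.2 alone would leave these conflicts standing.

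**Step 5. How many patients?** Section 4.1.1.4.5 gives adverse events of special interest in 16.1% of subjects in the two largest pembrolizumab studies: hypothyroidism 7.2%, infusion reaction 2.5%, hyperthyroidism 2.2%. Section 4.1 gives immune-mediated events in 13% of an NSCLC cohort. Applied to 57 patients:
- any event: 0.161 x 57 = 9.2; 0.13 x 57 = 7.4;
- at least one event other than those three: no less than 16.1 - 7.2 - 2.5 - 2.2 = 4.2%, and 0.042 x 57 = 2.4. Overlap between event types can only raise this figure, up to the 9.2 above;
- stopping treatment for such an event: 0.026 x 57 = 1.5.

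These counts include events too mild for steroids and events that 5.6 discontinues anyway. The documents give no split by grade, steroid need or length of hold, so the number for whom 5.3.2 decides the outcome cannot be derived.

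**The case against.** The strongest reply is that the text can be read in harmony. The ECI list is introduced by a word that need not be exhaustive, and an exception for events of suspected immunologic origin makes little sense unless the drafters had immune events in mind. The removal rule says should, Section 5.3 says only that discontinuation may be required and leaves the final decision on supportive therapy to the investigator or primary physician, and 5.3.2 ends with "Subjects may receive other medications that the investigator deems to be medically necessary".

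Part of this stands. Removal is not mandatory as worded, and nothing suggests that a patient would be denied steroids. But Section 5.3.1 treats Section 7.2 as the definition, no further immune event is named, and ECIs carry 24-hour reporting to the Sponsor, so reading every immune event as an ECI would silently widen that duty. The closing sentence concerns medications other than those prohibited. The physiologic-dose exception does not describe treatment courses with tapers of at least 4 weeks. None of these clauses says whether a patient treated under 5.4.1 stays on the trial.

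A reader might also infer that removed patients are lost to response assessment, so that each costs 1/28 = 3.6 or 1/29 = 3.4 percentage points of a cohort's response rate. The documents do not support that. Section 5.6 continues disease follow-up after discontinuation for reasons other than progression, and Section 7.1.5.1.2 sets imaging every 6 weeks, then every 9 weeks after 1 year. A response already recorded is not erased by later removal. What remains is that 5.3.2 does not tie its removal wording to this follow-up, and that the scan interval differs from the 8 weeks used on treatment.

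**Conclusion.** The inconsistency is real and limited. As written, Section 5.3.2 says that patients with steroid-treated Grade 2 pneumonitis, diarrhea/colitis, hypophysitis, nephritis or most hepatic events should be removed, while Table 3 lets them resume pembrolizumab. It matters mainly when the interruption is 21 days or less. The stronger reading, that every patient treated under 5.4.1 must be removed, goes further than the text.

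The number affected is probably a few of 57. That is a judgement: the background rates come from pembrolizumab studies without the vector or SBRT, and they lack the split needed. No effect on the response rate is demonstrated. The main consequence is inconsistent treatment continuation and a toxicity-related discontinuation rate that depends on which section was followed. This is an internal inconsistency, not a design flaw: it changes no hypothesis, sample size or endpoint definition. It should be corrected because it concerns an expected toxicity and is easily settled.

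**What to change.** Reconcile Sections 5.3.2, 5.4.1, 5.2.1.2 (with Table 3), 5.6 and 7.2.3.2 so that one list defines the events for which steroid use is compatible with staying on trial. Either 5.3.2 cites the events named in 5.4.1 and Table 3 in place of the ECI term, or the ECI list is aligned with them; the second route also changes reporting duties. Settle the Grade 3-4 and 21-day versus 12-week differences in the same amendment.

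State in 5.3.2 that removal means stopping study treatment with follow-up under Sections 5.6 and 7.1.5.1.2, if that is what is intended. The sponsor must decide which clinical rule applies. The cost is one wording amendment, with no added procedures or patients.

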5.4 Rescue Medications & Supportive Care

5.4.1 Supportive Care Guidelines

Subjects should receive appropriate supportive care measures as deemed necessary by the treating investigator. Suggested supportive care measures for the management of AEs with potential immunologic etiology are outlined below. Where appropriate, these guidelines include the use of oral or IV treatment with corticosteroids as well as additional anti-inflammatory agents if symptoms do not improve with administration of corticosteroids. Note that several courses of steroid tapering may be necessary as symptoms may worsen when the steroid dose is decreased. For each disorder, attempts should be made to rule out other causes such as metastatic disease or bacterial or viral infection, which might require additional supportive care. The treatment guidelines are intended to be applied when the investigator determines the events to be related to pembrolizumab.

Note: if after the evaluation the event is determined not to be related, the investigator does not need to follow the treatment guidance (as outlined below). Refer to Section 5.2.1.2 for dose modification.

It may be necessary to perform conditional procedures such as bronchoscopy, endoscopy, or skin photography as part of evaluation of the event.

- **Pneumonitis:**

- For **Grade 2 events**, treat with systemic corticosteroids. When symptoms improve to Grade 1 or less, steroid taper should be started and continued over no less than 4 weeks.
- For **Grade 3–4 events**, immediately treat with IV steroids. Administer additional anti-inflammatory measures as needed.
- Add prophylactic antibiotics for opportunistic infections in the case of prolonged steroid administration.

- **Diarrhea/Colitis:**

Subjects should be carefully monitored for signs and symptoms of enterocolitis (such as diarrhea, abdominal pain, blood or mucus in stool, with or without fever) and of bowel perforation (such as peritoneal signs and ileus).

- All subjects who experience diarrhea/colitis should be advised to drink liberal quantities of clear fluids. If sufficient oral fluid intake is not feasible, fluid and electrolytes should be substituted via IV infusion. For Grade 2 or higher diarrhea, consider gastrointestinal consultation and endoscopy to confirm or rule out colitis.
- For **Grade 2 diarrhea/colitis**, administer oral corticosteroids.
- For **Grade 3 or 4 diarrhea/colitis**, treat with IV steroids followed by HD oral steroids.
- When symptoms improve to Grade 1 or less, steroid taper should be started and continued over no less than 4 weeks.

- **T1DM if new onset (including diabetic ketoacidosis) or \geq Grade 3 hyperglycemia if associated with ketosis (ketonuria) or metabolic acidosis**

- For **T1DM** or **Grade 3–4 Hyperglycemia**
 - Insulin replacement therapy is recommended for T1DM and for Grade 3–4 hyperglycemia associated with metabolic acidosis or ketonuria.
 - Evaluate patients with serum glucose and a metabolic panel, urine ketones, glycosylated hemoglobin, and C-peptide.

- **Hypophysitis:**

- For **Grade 2 events**, treat with corticosteroids. When symptoms improve to Grade 1 or less, steroid taper should be started and continued over no less than 4 weeks. Replacement of appropriate hormones may be required as the steroid dose is tapered.
- For **Grade 3–4 events**, treat with an initial dose of IV corticosteroids followed by oral corticosteroids. When symptoms improve to Grade 1 or less, steroid taper should be started and continued over no less than 4 weeks. Replacement of appropriate hormones may be required as the steroid dose is tapered.

- **Hyperthyroidism or Hypothyroidism:**

Thyroid disorders can occur at any time during treatment. Monitor patients for changes in thyroid function (at the start of treatment, periodically during treatment, and as indicated based on clinical evaluation) and for clinical signs and symptoms of thyroid disorders.

- **Grade 2** hyperthyroidism events (and **Grade 2–4** hypothyroidism):
 - In hyperthyroidism, non-selective beta-blockers (e.g., propranolol) are suggested as initial therapy.
 - In hypothyroidism, thyroid hormone replacement therapy with levothyroxine or liothyronine is indicated per standard of care.
- **Grade 3-4** hyperthyroidism
 - Treat with an initial dose of IV corticosteroid followed by oral corticosteroids. When symptoms improve to Grade 1 or less, steroid taper should be started and continued over no less than 4 weeks. Replacement of appropriate hormones may be required as the steroid dose is tapered.

- **Hepatic:**

- For **Grade 2** events, monitor liver function tests more frequently until returned to baseline values (consider weekly).
 - Treat with IV or oral corticosteroids
- For **Grade 3–4** events, treat with IV corticosteroids for 24 to 48 hours.
- When symptoms improve to Grade 1 or less, a steroid taper should be started and continued over no less than 4 weeks.

- **Renal Failure or Nephritis:**

- For **Grade 2** events, treat with corticosteroids.
- For **Grade 3–4** events, treat with systemic corticosteroids.
- When symptoms improve to Grade 1 or less, steroid taper should be started and continued over no less than 4 weeks.

- **Management of Infusion Reactions:** Signs and symptoms usually develop during or shortly after drug infusion and generally resolve completely within 24 hours of infusion completion.

Table 4 shows treatment guidelines for subjects who experience an infusion reaction associated with administration of pembrolizumab (MK-3475).

Table 4 Infusion Reaction Treatment Guidelines

NCI CTCAE Grade	Treatment	Premedication at subsequent dosing

Grade 1 Mild reaction; infusion interruption not indicated; intervention not indicated
	
Increase monitoring of vital signs as medically indicated until the subject is deemed medically stable in the opinion of the investigator.
	
None

Grade 2 Requires infusion interruption but responds promptly to symptomatic treatment (e.g., antihistamines, NSAIDS, narcotics, IV fluids); prophylactic medications indicated for ≤24 hrs
	
Stop Infusion and monitor symptoms. Additional appropriate medical therapy may include but is not limited to: IV fluids Antihistamines NSAIDS Acetaminophen Narcotics
 
Increase monitoring of vital signs as medically indicated until the subject is deemed medically stable in the opinion of the investigator. If symptoms resolve within one hour of stopping drug infusion, the infusion may be restarted at 50% of the original infusion rate (e.g., from 100 mL/hr to 50 mL/hr). Otherwise dosing will be held until symptoms resolve and the subject should be premedicated for the next scheduled dose.
 
Subjects who develop Grade 2 toxicity despite adequate premedication should be permanently discontinued from further trial treatment administration.
	
Subject may be premedicated 1.5 hr (± 30 minutes) prior to infusion of pembrolizumab (MK-3475) with:
 
Diphenhydramine 50 mg p.o. (or equivalent dose of antihistamine).
 
Acetaminophen 500-1000 mg p.o. (or equivalent dose of antipyretic).


Grades 3 or 4
 
Grade 3: Prolonged (i.e., not rapidly responsive to symptomatic medication and/or brief interruption of infusion); recurrence of symptoms following initial improvement; hospitalization indicated for other clinical sequelae (e.g., renal impairment, pulmonary infiltrates)
 
Grade 4: Life-threatening; pressor or ventilatory support indicated
	
Stop Infusion. Additional appropriate medical therapy may include but is not limited to: IV fluids Antihistamines NSAIDS Acetaminophen Narcotics Oxygen Pressors Corticosteroids Epinephrine
 
Increase monitoring of vital signs as medically indicated until the subject is deemed medically stable in the opinion of the investigator. Hospitalization may be indicated.
 
Subject is permanently discontinued from further trial treatment administration.
	
No subsequent dosing

Appropriate resuscitation equipment should be available in the room and a physician readily available during the period of drug administration.
		

IV = intravenous; NSAID = nonsteroidal anti-inflammatory drug; p.o. = orally.

